3.4 Study outcomes

3.4.1 Primary study outcomes

For this study, wasting will be defined by $WHZ < -2$ (relative to the WHO reference of 2006) or $MUAC < 125$ mm or bilateral edema. Moderate wasting (MAM) will be defined by $-3 \leq WHZ < -2$ (relative to WHO reference of 2006) or $115 \leq MUAC < 125$ mm. Severe wasting (SAM) will be defined by $WHZ < -3$ (relative to WHO 2006 reference) or $MUAC < 115$ mm or bilateral edema.

The primary outcomes of the study will be:

1. Longitudinal prevalence of wasting among children enrolled at 6 months of age followed monthly until the end of the study (cohort 1). This indicator is defined for each child as the number of visits during which wasting is observed divided by the total number of monthly visits made (by interviewers).

⁴ Gould, W. W. 2012a. Using Stata's random-number generators, part 2: Drawing without replacement. The Stata Blog:

Not Elsewhere Classified. <http://blog.stata.com/2012/08/03/using-statas-random-number-generators-part-2-drawing-without-replacement/>.

2. The recovery rate in children enrolled at [6-23] months of age for up to 3 months of treatment in a treatment unit and followed through to discharge (cohort 2). This indicator was initially defined in the protocol as the number of discharges considered cured according to national program criteria (WHZ>-2 and MUAC>=125mm and absence of bilateral edema for two consecutive visits, within 12 weeks of enrollment in the program) divided by the total number of exits recorded. Due to COVID-19 modifications in the implementation of the national protocol, children are discharged based on the MUAC criteria only, after only one visit, and WHZ is not measured. We therefore redefined this indicator as the number of discharges with MUAC>=125mm within 12 weeks of enrollment in the program, divided by the total number of exits recorded.
3. The incidence of wasting in children enrolled at [6-23] months of age at discharge from a wasting treatment program and followed for 6 months (Cohort 3). This indicator is defined as the number of new cases of wasting recorded during monthly visits.

3.4.2 Secondary study outcomes

Secondary outcomes of the study include:

For Cohorts 1 and 3 :

- The longitudinal prevalence of :
 - Wasting, defined as above (cohort 3)
 - MAM, defined for each child as the number of MAM diagnoses divided by the total number of monthly visits made
 - SAM, defined for each child as the number of SAM diagnoses divided by the total number of monthly visits made
- The incidence of :
 - Wasting, defined as above (cohort 1).
 - MAM, defined as the number of new MAM cases recorded during monthly visits.
 - SAM, defined as the number of new SAM cases recorded during monthly visits.
- The prevalence of anemia defined as the proportion of children with a hemoglobin level below 11g/dl at the end of the study.
- Mean hemoglobin concentration at the end of the study.
- Prevalence of stunting defined as the proportion of children with HAZ <-2 (relative to the 2006 WHO reference) at the end of the study.
- The average z-scores HAZ at the end of the study.
- Wasting screening coverage defined as the proportion of children screened (using MUAC, weight-for-height or bilateral edema) in the month prior to the monthly visit. Two sub-outcomes will also be considered:
 - Screening coverage by care groups.
 - Screening coverage of the family MUAC component, which is the screening performed by a family member in the past month.
- Linear growth rate defined as the change in height-for-age index per month.
- Speed of weight growth defined as the change in weight-for-height index per month.
- Weight gain defined as the weight change per month.
- MUAC gain defined as the change in MUAC per month.

- The longitudinal prevalence of childhood morbidity, i.e. acute respiratory infections, fever, diarrhea and malaria, defined as the number of reports of signs of these morbidities divided by the total number of days reported (1-3 per monthly visit made).
- Mother/guardian's knowledge of nutrition, WASH, and health expressed as cumulative total and domain scores at exit.
- Infant and young child feeding (IYCF) practices:
 - Introduction of (semi) solid and soft complementary foods .
 - Minimum dietary diversity in children, defined as the proportion of children who consumed at least 5 of the 8 food groups (including breast milk) the day before the survey.
 - Minimum meal frequency for children, defined as the proportion of children who had eaten the day before the survey: 2 meals for breastfed children 6-8 months, 3 meals for breastfed children 9-23 months, or 4 meals for non-breastfed children 6-23 months.
 - Minimum acceptable diet, defined as the proportion of children with both minimal dietary diversity and minimal meal frequency on the day before the survey.
 - Consumption of iron-rich or iron-fortified foods in children.
- Practices related to water, hygiene and sanitation, as per Standard USAID indicators related to drinking water source, treatment, storage; hand washing; and sanitation
- Vaccination coverage, defined as the proportion of children with complete vaccination for their age.

For Cohort 2⁵:

- Nutritional status (measured by MUAC) at admission in treatment unit.
- The duration of treatment defined as the number of days spent on treatment (between admission and discharge).
- Treatment adherence defined as the proportion of cases enrolled for treatment who received timely treatment from dedicated services until recovery.
- The treatment outcome (drop-out, death, transfer, non-response rates).
- longitudinal prevalence of childhood morbidity defined by the number of days for which signs of these morbidities were reported divided by the total number of days observed/reported in the recall periods.

3.4.3 Auxiliary outcomes

In addition to these study outcomes, the impact of the package on three auxiliary study outcomes will also be assessed in cohort 1 and 3. They are not reported as formal study outcomes because of the imprecision of their estimate or the small size. These outcomes will be considered in an exploratory manner:

⁵ All the results cited below will be collected from the registers (including follow-up sheet) of the wasting treatment services (without collecting personal information of mothers/children, such as names, addresses, date of birth, telephone nr.). There will therefore be no data collection from mothers/children attending the consultations.

- i) Enrollment of MAM and SAM cases defined as the proportion of cohort 1 or cohort 3 children screened positive in the month prior to the monthly visit (conducted by the survey teams) who were enrolled in a wasting treatment program.
- ii) Treatment coverage defined as the proportion of cohort 1 children with SAM and/or MAM under treatment as recalled by the child's caregiver

Results i) and ii) will be strongly influenced, in both study groups, by the MAM/SAM cases referred by the survey teams who will record anthropometry during monthly visits. In the case of SAM, which is a life-threatening condition, the investigators must for ethical reasons refer children from both study groups to the health center to initiate treatment. Thus, the real impact of the intervention on enrollment and treatment coverage may be underestimated.

3.5 Sample Size

3.5.1 Cohort 1 – primary outcome: longitudinal prevalence of wasting

The main cohort (#1) will include 1,750 children in the community aged 6 to 6.9 months, included for a period of 7 months and followed up monthly until the end of the study (total duration: 9 months).

The main cohort (#1) will include children aged 6-6.9 months. Given the small size of most villages and the sample size needed to detect a significant, plausible and meaningful difference in longitudinal wasting prevalence (primary outcome) between groups, we have calculated that we need to include an average of 3 children per month for 7 months in the 50 largest villages (25 villages in the control group and 25 in the intervention group) and an average of 2 children per month for 7 months in the 50 smallest villages in the study area (i.e., the medium-sized villages in the Mongo Health District: equally 25 in the control group and 25 in the intervention group). The children will all leave the cohort in the same month: counting the month of inclusion, the children will be seen for a maximum of 9 months (for children included at the start of the study) and a minimum of 3 months (for children included during the 7th month). This will result in a total sample of 1,750 children (10,500 visits in total of which 1,750 inclusions and 8,750 follow-ups). With 15% dropout, **the size of this study would provide sufficient power to detect a relative decrease of about 35% in the longitudinal prevalence of wasting**, with a power of 80% and a statistical significance of 5%, taking into account the cluster effect at the village level and the imbalance in cluster size.

3.5.2 Cohort 2 - primary outcome: recovery rate

The treatment Cohort (#2) will include all 6-23 months old children living in the 100 study villages and registered for treatment, based on health system records.

Using 2019 health district statistics, the total number of SAM cases (6-23 months of age) over 9 months of follow-up was estimated at 3,928. We assumed the number of MAM cases would be at least as many.

With 100 clusters that each have an average of 78 cases of SAM and MAM over a 9-month period, assuming a recovery rate of 85%, a statistical power of 80%, a type I error of 5% and an intra-cluster coefficient of 0.05, **a minimum difference of ~5 percentage points in the recovery rate could be detected in children aged 6-23 months.**

3.5.3 Cohort 3 - Primary Outcome: incidence of relapse

The relapse prevention cohort (#3) will include 700 [6-23] months old children living in the 100 villages in the study area, who were discharged from treatment and recovered from wasting, and will be followed up monthly for 6 months.

Given the small size of most villages and the required sample size, we have calculated that we need to enroll 8 children in the 50 largest villages and 6 children in the 50 average villages and follow them every month for 6 months each. This will result in a total sample size of 700 children (4,900 visits in total, including 700 inclusions and 4,200 follow-ups). **Such a sample size would provide sufficient power to detect a decrease of about 33% in the incidence of relapse.**

3.6 Sampling and study inclusion criteria

Details on the selection of children, inclusion and exclusion criteria, and changes to the protocol, are given in Table 2.

Table 2: Selection of study participants, inclusion and exclusion criteria, sample size and follow-up details for the 3 study cohorts.

	Main cohort	Treatment cohort	Relapse prevention cohort
Selection of participants	In each village, random selection from a randomly ordered census list of children aged 0-6 months (census conducted by the survey team in the first month of the survey), prepared by an investigator based in Dakar using Stata software. Children not meeting inclusion criteria (see below) will be replaced until the maximum number of children is met (3 times the number of months of inclusion), or until the list of eligible children is exhausted.	All records of children (aged [6-23] months) living in the 100 most populated villages in the study area and admitted during the study in a treatment program by the national CMAM program. Treatment data will be collected by the CMAM treatment units as part of their routine. Each treatment unit will be visited by an enumerator who will be responsible for monitoring data quality and copying anonymous data from the registers to electronic forms.	All available children in each village who will be discharged from CMAM treatment (based on treatment unit registers) and recovered will be invited to participate in the study until the required sample size is reached for each village (8 children). In villages with more children than necessary, the study team will invite children to participate in the order of a randomly ordered list prepared by an investigator based in Dakar using Stata software.
Inclusion criteria	6-6.9 months of age. Child singleton. Resident of the village. Consent of the mother or guardian.	Child admitted for treatment in a national treatment program. 6-23 months of age at admission. Child lives in one of the 100 villages in the study area.	Child has been successfully treated for wasting (defined as MUAC ≥ 125 mm) and has been discharged from the national treatment program within the last 30 days. 6-23 months of age at inclusion. Child singleton.

	Main cohort	Treatment cohort	Relapse prevention cohort
			Resident of the village. Consent of the mother or guardian.
Exclusion criteria	Congenital malformations that make anthropometric measurements impossible. Mother intends to leave the study area by December 2021.	None.	Congenital malformations that make anthropometric measurements impossible. Mother intends to leave the study area by December 2021.
Sample size	1,750 children	Exhaustive inclusion	700 children
Intended duration of inclusion	7 months	9 months	2 months
Follow-up frequency	Monthly	Bi-monthly visit by enumerators to health center treatment units, and monthly visits to community treatment units.	Monthly
Intended study duration	enrolled children will be followed until the end of the study, with a total study duration of 9 months	from program admission to program exit, with a total study duration of 9 months.	Follow-up of all children for 6 months, with a total study duration of 8 months.
Changes to the protocol	November 2021: Study duration was increased by a month and exits were split evenly across the 2 last months of the study, based on enrollment order.	November 2021: Study duration was increased by a month.	November 2021: To meet the sample size, we extended the inclusion duration to 7 months January 2022: To meet the sample size, we extended the inclusion duration to 9 months, and we released the limitation on the maximum number of children per village. We also extended the total study to 12 months, and enrolled children will be followed-up either for 6 months, or until the end of the study, whatever comes first.

4 Data management

The management of all research data will follow IFPRI's institutional research data management protocol, overseen by the IFPRI Data Governance Committee, as well as UNICEF data governance standards. All received data will be carefully anonymized and de-identified so that the privacy of participants and research subjects is fully protected. Personally Identifiable Information data (PII; names, telephone

numbers, GPS coordinates, date of birth) will be stripped from the research data when receiving the data on the server. During data collection, PII data will be stored in a separate secured server folder accessible only to the Principal Investigators. PII data will only be used to identify a household to conduct additional verification of previously collected data. When data collection and data validation have been completed, PII data will be destroyed.

In accordance with IFPRI's policy on research data management and open access, at the time of publication of scientific articles presenting the primary results, fully anonymized databases will become a public good and will therefore be made available to the scientific community, government, partners.

All data collection is scheduled to start once the study trial is registered on clinicaltrials.gov.

5 Variables creation

5.1 Variables creation for cohorts 1 and 3

Age will be calculated in days counting the number of days between the date of birth and the date of data collection. Date of birth will be collected at enrollment from each child's health booklet and, if not available, from a vaccination card or any other written record. When no written record will be available, date of birth will be estimated by the enumerator using a detailed calendar of local events.

All weight, length and MUAC measurements will be taken in duplicate by a trained enumerator and a trained assistant, and a third measurement will be taken if the difference between the two repeated measurements is >5mm for length and MUAC and >300g for weight. The average of the two closest repeated measurements will be used for the calculation of nutritional status indicators.

The child weight-for-height and height-for-age z-scores will be calculated using the `zscore06` command in Stata (15), which uses the World Health Organization's growth standard (16).

A wasting episode will be defined as follows: it starts when a child is found to be wasted at the monthly survey and ends when a child does not suffer from wasting at one monthly measurement. MAM and SAM episodes will be defined the same way, except that children who qualify as MAM during the SAM recovery process will still be considered SAM and not MAM.

During follow-up visits, we will interview the caregiver about child morbidity (acute respiratory infections, diarrhea, fever, and malaria) over the previous 3 days. Diarrhea will be defined as recall of at least three loose stools in 24 hours, or of stools with blood. Fever (axillary temperature $> 37.5^{\circ}\text{C}$) will be measured by a thermometer and the history of fever for each of the 3 previous days will also be recalled. The presence of an acute respiratory infection (ARI) in the 3 previous days will be assessed by recalling the specific symptoms associated with ARI (cough, difficulty breathing, rapid breathing, wheezing). The presence of malaria parasites will be checked by enumerators with a rapid diagnostic test for malaria, if body temperature is above 37.5°C or if the mother reports a fever episode in the child within the last 72 hours.

The hemoglobin concentration will be measured at enrollment and at exit by spectrophotometry using a HemoCue 301 (HemoCue Ltd, Dronfield, UK), using a drop of capillary blood drawn from the child's finger.

Child anemia and severe anemia will be defined by hemoglobin concentrations of less than 11 g.dL⁻¹ and less than 7 g.dL⁻¹ respectively.

Screening will be defined as caregiver recall that MUAC was measured in the target child.

Single treatment coverage will be calculated at individual level on the sub-group of children with wasting and children recovering from wasting, using the formula:

$$\text{single coverage} = \frac{C_{in} + R_{in}}{C_{in} + R_{in} + C_{out} + R_{out}}$$

where C_{in} = current wasting, SAM or MAM cases under treatment, C_{out} = current wasting, SAM or MAM cases not under treatment, R_{in} = recovering wasting, SAM or MAM cases under treatment, and R_{out} = recovering wasting, SAM or MAM cases not under treatment. Children with wasting and recovering children will be identified using the anthropometric measures. Recovering children will be defined as children with wasting the previous month but not wasted the current month.

Principal component analysis will be used to generate a household wealth status score (17). We will include household-level data on materials used in housing roofs, floors, and walls, occupational status of the housing, the main source of light, and assets owned by 5 to 95% of the study sample at enrollment. Tertiles of loadings on the principal component with the highest eigenvalue will be used.

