When community workers screen a child for acute malnutrition, the child is: i) either diagnosed as negative (code green, MUAC ≥ 125 mm); ii) or diagnosed as MAM positive ($115\text{mm} \leq \text{MUAC} < 125\text{mm}$, code yellow); iii) or diagnosed as SAM positive (MUAC $< 115\text{mm}$ or bilateral edema, code red). In the case of SAM, the mother-child couple is referred to the health center for confirmation of the diagnosis based on the MUAC and initiation of treatment. If the diagnosis is confirmed, the child is examined to verify the presence or absence of medical complications. Following the COVID19 pandemic, only the MUAC criterion is currently used to screen children.

In the absence of signs of complication, the MAM child is admitted to an outpatient program (UNS or FARNE) with a scheduled follow-up every two weeks. The duration was extended following the COVID19 pandemic; follow-up is currently monthly. The mother receives a ration of food supplements to be given to the child every day (RUSF or CSB++). In the absence of complications, and after a successful appetite test, the SAM child is included in an outpatient treatment program (UNA) with follow-up scheduled every week. The duration was extended following the COVID19 pandemic; follow-up is currently every two weeks. The mother receives a ration of food supplements (RUSF) to be given to the child every day. Complicated cases of SAM or MAM or cases with edema are referred for inpatient treatment at the hospital which has a pediatric ward (UNT ward).

Children are discharged from these treatment programs if they reach a weight-for-height->-2 z-scores and a MUAC ≥ 125 mm and the absence of bilateral edema for two consecutive visits.

c) Psycho-cognitive stimulation program at UNA/UNT

During the rehabilitation of children under treatment at UNA/UNT, their psycho-cognitive stimulation should begin, and continue after discharge, to reduce the risk of mental and physical sequels. Psychosocial stimulation should be done by the doctor and nurses. The social worker is in charge of organizing the sessions.

This program includes activities such as :

- Organizing sessions to teach mothers how to make toys themselves with cheap and salvageable materials;
- Organizing training sessions to teach mothers the importance of games and discovery in providing the psycho-cognitive and physical stimulation the child needs (this is an integral part of the treatment);

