3.2 Study design

We designed a two-arm, cluster-randomized, non-blinded, longitudinal, effectiveness trial to study the impact of the PASIM intervention as compared to the standard of care in the study area. Two study groups will be formed, a control/comparison group, and an intervention group receiving the integrated package of interventions. The activities of the control and intervention group are summarized in Table 1.

Table 1: intervention package in intervention and comparison groups

	Intervention	Comparison
Prevention	Integrated community care group (CCG) Weekly home visits: BCC (pregnancy to 23 mo) Monthly village-level distribution in presence of CCG volunteer of 360 g of soap + 1 L of bleach + 3 kg of CSB++ (non wasted 6-11 mo) MNPs (12-23 mo)	No intervention (some pre-existing CCG with no support since 2019; some areas with punctual preventive interventions)
Screening	Family MUAC (6-23 mo) Integrated CCG (6-23 mo) Weekly home visits: training and supervision of family MUAC, MUAC screening, referral, follow-up on referral through supervisor (NGO promoter)	No intervention (Contact with existing CCG and health system ; some areas with caregivers trained to family MUAC in 2019)
Treatment	Current CMAM protocol (adapted), health center or community site (6-59 mo) SAM/MAM treatment, MUAC only, reduced intensity, culinary demonstrations at community sites Strengthened RUTF/RUSF supply chain Integrated CCG (6-23 mo) Weekly home visits: general and AM specific counselling, ensure RUSF/RUTF compliance Monthly village-level distribution in presence of CCG volunteer of 360 g of soap + 1 L of bleach (6-23 mo)	Same as for intervention group Strengthened RUTF/RUSF supply chain No intervention
Relapse prevention	Integrated CCG Weekly home visits: specific counselling on IYCF (6-23 mo for 6 mo) Monthly village-level distribution in presence of CCG volunteer of 200 g of soap + 400 mL of bleach + 3 kg of CSB++ (6-23 mo for 6 mo)	No intervention

Abbreviation used: BCC, Behavior Change Communication; CCG, Integrated community care group; CMAM, Community-based management of acute malnutrition; CSB++, improved corn-soy-blend for young children; MAM, Moderate wasting; MNPs, Micronutrients powder; MUAC, Mid-upper arm circumference; RUSF, Ready-to-use supplementary food; RUTF, Ready-to-use therapeutic food; SAM, Severe wasting.

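### Treatment coverage counts children wasted by weight-for-height alone as cases, although the programme screens and treats on MUAC, so the figure mixes uptake with a mismatch of thresholds

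*SAP*

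**What the plan says.** **Who is a case for coverage.** SAP 5.1 defines single coverage as (C_in + R_in) / (C_in + R_in + C_out + R_out). C_out is "current wasting, SAM or MAM cases not under treatment". On identification it says "Children with wasting and recovering children will be identified using the anthropometric measures", and on the R terms "Recovering children will be defined as children with wasting the previous month but not wasted the current month". No condition restricts these children to those whom the programme would admit. SAP 3.4.1 sets the case definition for the study: "wasting will be defined by $WHZ < -2$ (relative to the WHO reference of 2006) or $MUAC < 125$ mm or bilateral edema".

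**Status of the outcome.** SAP 3.4.3 lists "Treatment coverage defined as the proportion of cohort 1 children with SAM and/or MAM under treatment as recalled by the child's caregiver" among the auxiliary outcomes, to be treated as exploratory. SAP 6.4.2 extends the exploratory coverage analysis to cohort 3.

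**What the programme uses.** SAP 3.2 Table 1 describes treatment in the intervention arm as "SAM/MAM treatment, MUAC only, reduced intensity" and gives the comparison arm the same protocol. Protocol 3.1.2 says that "only the MUAC criterion is currently used to screen children". SAP 3.4.1 adds that units discharge on MUAC and do not measure WHZ. Protocol 4.4 gives the survey teams' referral rule for severe cases as MUAC <115 mm or oedema, again without WHZ.

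**What the plan does about the definition.** SAP 6.4.3 repeats the analysis under MUAC <125 mm or oedema, but for the primary outcomes of cohorts 1 and 3. SAP 3.4.3 warns that the impact on coverage may be underestimated, but gives survey-team referral as the only reason.

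**The concern.** The numerator depends on a programme that works by MUAC; the denominator is drawn by a wider rule. A child with WHZ <-2 and MUAC of 125 mm or more is a case for the study but not for the treatment units. Such a child normally counts in C_out while WHZ stays low, and in R_out the month after WHZ recovers.

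Cohort 3 shows this most plainly. SAP 3.6 Table 2 admits children discharged at MUAC of 125 mm or more within the last 30 days. One who enters with WHZ still below -2 is counted as a current case needing treatment soon after the programme has recorded recovery.

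The SAP has already moved to MUAC elsewhere: the recovery outcome of cohort 2, its nutritional status at admission, entry to cohort 3, and the definition of screening. Coverage was left on the wider definition.

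Protocol 3.4 asks what PASIM does to treatment coverage. A low figure could be read as failed referral or uptake when part of it reflects children whom neither arm's programme is set up to detect or admit. The contrast between arms would also depend on how many such children each arm has.

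**Working it through.** The plan gives no expected coverage, detectable difference or sample size for this outcome, so there is no figure to reproduce. The check is algebra on the SAP 5.1 formula.

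**1. Inputs.** For each arm:
- w = WHZ-only share of the whole denominator, current plus recovering
- c = coverage among MUAC or oedema cases
- t = coverage among WHZ-only cases

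The documents give none of these, so every value below is an assumption. As background only, Protocol 1 cites coverage below 25% in earlier studies in Mali and Burkina Faso, and Protocol 3.1.1 cites 37% for SAM care in Chad in 2015. SAP 6.4.1 plans linear probability models for binary outcomes, so the effect is an absolute difference.

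**2. Coverage in one arm.** Reported coverage = (1-w)c + wt. The shortfall against c is w(c-t), which is positive whenever w>0 and t<c.

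The share must be taken over the whole denominator. If current and recovering children stand at 2:1, 40% of current cases are WHZ-only and all recovering children are MUAC cases, then w = 0.40 × 2/3 = 26.7%. With t=0 the ceiling on coverage is 73.3%, not 60%.

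**3. Equal w in both arms, t=0.** Each arm and the absolute difference are multiplied by (1-w). Assumed c is 50% in the intervention arm and 30% in the control arm.

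| w | Intervention | Control | Difference | Ratio |
|---|---|---|---|---|
| 0 | 50% | 30% | 20 points | 1.67 |
| 20% | 40% | 24% | 16 points | 1.67 |
| 40% | 30% | 18% | 12 points | 1.67 |
| 60% | 20% | 12% | 8 points | 1.67 |

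**4. Some WHZ-only children in treatment.** Take c of 40% against 25% (true difference 15.0 points), w=35% in both arms, and t=0.3c. The multiplier is 0.65 + 0.35 × 0.3 = 0.755. Reported coverage is 30.2% against 18.9%, a difference of 11.3 points. With t=0 it would be 0.65 × 15.0 = 9.8 points.

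**5. Unequal w, t=0.** With subscripts I and C for the arms, the reported difference is (c_I - c_C) - (w_I c_I - w_C c_C). It is understated only if w_I c_I > w_C c_C. Keep 40% against 25% and w_C = 35%, so that control coverage is 0.65 × 25% = 16.25%.

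| w_I | Intervention | Reported difference | True difference |
|---|---|---|---|
| 45% | 22.0% | 5.8 points | 15.0 points |
| 35% | 26.0% | 9.8 points | 15.0 points |
| 25% | 30.0% | 13.8 points | 15.0 points |
| 20% | 32.0% | 15.8 points | 15.0 points |

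Break-even is w_I = 35% × 25/40 = 21.9%. Below that, the difference is overstated.

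**6. Cost of a smaller denominator.** Assume 300 cases per arm, w=35%, c of 40% against 25%, two-sided 5%, and no allowance for clustering or repeated visits. Restricting to 195 MUAC or oedema cases per arm gives power of about 89%. Keeping all 300, with coverage of 26.0% against 16.3%, gives about 83%. In this case dropping the WHZ-only children does not lose power.

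**The case against.** The strongest reply is that the proportion of all wasted children under treatment is a legitimate quantity and uses the same case definition as the primary outcome. That stands. Coverage is understated only if the target is children whom the programme can admit. The SAP does not say which target it intends, and that silence is part of the point.

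The outcome is also exploratory. Auxiliary outcome (i) in SAP 3.4.3 already reports enrolment among children who screened positive, so uptake among detected cases will be visible beside coverage. This limits the harm. It does not remove it, because outcome (i) leaves out eligible children who were never screened.

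The existing warning in SAP 3.4.3 does not help, since it concerns referral by the survey teams and not the threshold.

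A reader might infer more: that the arm difference must be understated, and that every visit of a WHZ-only child counts as uncovered. The documents support neither.
- The direction of the arm difference depends on the WHZ-only share in each arm, which is not given. A package built on MUAC screening, with the supplement limited to children who are not wasted by MUAC, could change that share.
- A child admitted on MUAC whose MUAC has since passed 125 mm, with WHZ still below -2 and discharge not yet reached, is counted in C_in. Protocol 3.1.2 has treatment visits every two weeks for SAM and monthly for MAM, so a survey visit can fall in that interval.

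**Conclusion.** The mismatch is documented, and nothing in the plan resolves it for coverage. Taken as coverage of programme-eligible children, the reported figure is too low in each arm whenever w>0 and t<c.

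The effect on the comparison is conditional. With equal w and t=0, the absolute difference shrinks by the factor (1-w) and the ratio is unchanged. With unequal w, the absolute difference can be biased in either direction. The size is unknown because the documents give no WHZ-only share for either arm; all figures above are illustrations.

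This is a minor point. No primary or secondary outcome and no sample-size claim is affected. It is worth correcting because the outcome answers a research question stated in the protocol and the correction is cheap.

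**What to change.** In SAP 3.4.3 and 5.1:

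- State the target population for coverage: programme-eligible children, all wasted children, or both.
- Compute the C and R terms also under the definition already in SAP 6.4.3, MUAC <125 mm or oedema. For the severity-specific versions of this analysis, use 115 ≤ MUAC <125 mm for MAM, and MUAC <115 mm or oedema for SAM. Half-open limits matter because averaged duplicate readings can fall between whole millimetres. Keep the SAP 5.1 rule that a child passing through MAM while recovering from SAM remains SAM.
- Label this result coverage of programme-eligible children. Report it beside the WHZ-inclusive figure, labelled coverage of all wasted children.
- Show the WHZ-only share of the denominator by arm, so that a reader can see how far the two versions should differ.

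The cost is a change of wording and one extra analysis. The anthropometry is already recorded at the monthly visits, so no new data are needed. The denominator becomes smaller. The change concerns the analysis definition only; no admission, referral or treatment rule is touched.
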